10.4.4 Baseline Descriptive Statistics

Baseline demographic characteristics will be reported.

10.4.5 Planned Interim Analyses

As indicated in the two-stage design (Section **10.2**), the number of responses after 12 evaluable checkpoint naïve participants have been treated will be noted and will be used to determine if enrollment to the second stage of accrual may proceed. After the first restaging scan of the last evaluable patient required for the interim analysis, enrollment to the checkpoint naïve cohort will be halted to allow for an analysis by the study statistician. An interim analysis report will be created by the study statistician to document the number of responses in the first stage and will be reviewed by the PI and study team. The memo will be provided to and approved by the study sponsor prior to continuation of accrual. Alternatively, if the required number of responses is observed before that time, the memo may be generated, reviewed and provided to the study sponsor at that point without a pause in accrual.

The interim analysis report will also be provided to the DSMB.

10.4.6 Tabulation of Individual Participant Data

Individual responses may be depicted using a waterfall plot or a spider diagram. In addition, to assess feasibility, the participant description of symptomatic adverse events (complimentary to clinician reported CTCAE) and missing data will be tabulated.

10.4.7 Exploratory Analyses

The exploratory objectives are intended to collect data for use in planning future scientific investigations or clinical research. These analyses are expected to be performed only using descriptive techniques, reporting descriptive statistics including confidence intervals when appropriate. Any statistical tests performed for evaluation of exploratory objectives will be done without formal adjustment for multiple comparisons, but in the context of the number of tests performed.

11 COLLABORATIVE AGREEMENTS

11.1 COOPERATIVE RESEARCH AND DEVELOPMENT AGREEMENT (CRADA)

A CRADA (02666) is in place with EMD Serono for the supply of bintrafusp alfa.

12 HUMAN SUBJECTS PROTECTIONS

12.1 RATIONALE FOR SUBJECT SELECTION

Subjects from all racial/ethnic groups are eligible for this study if they meet the eligibility criteria. Efforts will be made to extend accrual to a representative population. Due to impaired cellular immunity which may affect the efficacy of treatment, participants with poorly controlled HIV as well as patients with detectable viral loads of hepatitis B and C will be excluded.

As there is a risk of severe bleeding with this study drug, participants must be willing to receive blood transfusions if medically necessary for their own safety. Participants must be able to receive blood transfusions in order to minimize the risks of receiving bintrafusp alfa.

12.2 PARTICIPATION OF CHILDREN

Individuals under the age of 18 will not be eligible to participate in this study because of unknown toxicities in pediatric participants.

The effects of bintrafusp alfa on the developing human fetus are unknown. For this reason and because immunotherapeutic agents as well as other therapeutic agents used in this trial may be teratogenic, women of child-bearing potential and men must agree to use highly effective contraception (hormonal or barrier method of birth control; abstinence) prior to study entry and up to 65 days for women and 125 days for men following the last dose of any study treatment. Should a woman become pregnant or suspect she is pregnant while she or her partner is participating in this study, she should inform her treating physician immediately.

12.3 PARTICIPATION OF SUBJECTS UNABLE TO GIVE CONSENT

Adults unable to provide consent are excluded from enrolling in the protocol. However, it is possible that subjects enrolled in the protocol may permanently lose the capacity to consent for themselves during the course of this study. In the event this occurs, the subjects will be removed from treatment and remain in the study to be followed-up for overall survival. Due to the rarity of ONB, it is important to keep any enrolled subjects in follow-up for overall survival to learn more about the outcome of the disease. All subjects \geq age 18 will be offered the opportunity to fill in their wishes for research and care, and assign a substitute decision maker on the “NIH Advance Directive for Health Care and Medical Research Participation” form so that another person can make decisions about their medical care in the event that they become incapacitated or cognitively impaired during the course of the study.

Note: The PI or AI will contact the NIH Ability to Consent Assessment Team (ACAT) for evaluation to assess ongoing capacity of the subjects and to identify a LAR, as needed.

Please see Section [12.6.1](#) for consent procedure.

12.4 EVALUATION OF BENEFITS AND RISKS/DISCOMFORTS

Participants will receive evaluation of their disease at the National Cancer Institute's Clinical Center. The potential benefit to a participant that goes onto study is a reduction in the bulk of their tumor which may or may not have a favorable impact on symptoms and/or survival.

Potential adverse reactions attributable to the administration of the study drug utilized in this trial are discussed in Section [14.1.2](#). All care will be taken to minimize side effects, but they can be unpredictable in nature and severity. Participants will be examined and evaluated prior to enrollment. All evaluations to monitor the treatment of participants will be recorded in the medical record. If participants suffer any physical injury as a result of the participation in this study, immediate medical treatment is available at the Clinical Center, National Cancer Institute, Bethesda, Maryland.

Although no compensation is available, any injury will be evaluated and treated in keeping with the benefits or care to which participants are entitled under applicable regulations.

12.5 RISK/BENEFIT ASSESSMENT

12.5.1 Known Potential Risks

12.5.1.1 Potential Risks Associated with Bintrafusp alfa

Potential adverse reactions attributable to the administration of the study drugs utilized in this trial are discussed in Section [14.1.2](#). Risks include the possible occurrence of any of a range of side effects which are listed in the Consent Document or this protocol document. Frequent monitoring for adverse effects will help to minimize the risks associated with administration of the study agents.

Participants may be harmed from being in this study by toxicity due to the drug or combination of drugs given during this study. M7824 is similar to immune check point inhibitors. There are preliminary data to suggest that not all patients benefit from immune check point inhibitors nor M7824. Additionally, there are preliminary data to suggest that an unexpectedly rapid progression of disease occurs in some patients receiving immunotherapy such as immune checkpoint inhibitors.

12.5.1.2 Risk of Optional Biopsies

All care will be taken to minimize risks that may be incurred by tumor sampling. There are potential risks associated with this procedure including pain or bleeding caused by the anesthesia needle as well as the biopsy procedure itself. An allergic reaction to the local anesthetic may occur. There may be bruising at the site of biopsy. Continuous bleeding and infection are rare and very often is easily controlled. Potential risks and discomforts will be minimized to the greatest extent possible by using personnel with appropriate training and monitoring.

12.5.1.3 Risks Due to Radiation

The study will involve radiation from the following sources:

- Up to 7 CT scans (C/A/P) per year for disease assessment
- Up to 3 FDG or Dotatate PET/CT scans per year for disease assessment
- 3 CT-guided biopsies

- Up to 2 bone scans

Subjects in this study may be exposed to approximately 14.28 rem maximum annually.

The radiation exposure that participants may get in this study will expose them to the roughly the same amount of radiation as 47.6 years of background radiation. The risk of getting cancer from the radiation exposure in this study is 1.4 out of 100 (1.4%) and of getting a fatal cancer is 0.7 out of 100 (0.7%).

Note: As the FDG PET/CT scans have a higher possible radiation exposure than Dotatate PET/CT, this scan was used in the possible maximum radiation exposure above and in the informed consent document.

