6. Subsequent Post-treatment follow-up: Every 3 months (+/- 2 weeks), starting after the safety visit for the first year, followed by every 6 months (+/- 4 weeks) for years 2-5, and then annually (+/- 6 weeks) thereafter at the discretion of the investigator. Follow-ups may be done by phone/email or by clinic visit at the discretion of the investigator. Follow-up via telephone/email will include survival, adverse events, and assessment of further tumor therapy; furthermore, routine outside blood, urine, and imaging results may be collected and used for analysis at the discretion of the investigator. Any other evaluations and tests should be performed as clinically indicated. Participants who have not progressed on treatment will be scanned until progression. Those that completed the previous 26-doses course and have progression will be invited for an additional course (26 doses) at the time of progression.
7. Bintrafusp alfa administered IV at flat dose of 1,200 mg.
8. As indicated in Section **12.3**, all subjects will be offered the opportunity to complete an NIH advance directive form. This should be done preferably at baseline but can be done at any time during the study as long as the capacity to do so is retained. The completion of the form is strongly recommended but is not required.
9. Every 6 weeks.
10. Imaging (Section **6.3**) will be performed every 8 weeks (+/- 1 week). In the event of a PR or CR, tumor imaging assessments may be performed every 3 months (+/- 2 weeks) at the discretion of the investigator. Tumor assessment should be continued beyond end of treatment in participants who have not experienced PD until they experience PD in order to assess PFS. Additional imaging to be performed at the investigator's discretion. Imaging performed in outside facilities maybe utilized in the case of travel restrictions or delays, airport closures, inclement weather, family responsibilities, security alerts and government holidays, etc. Nuclear bone scan or imaging may be done for individuals with known/suspected bone lesions at screening; in these cases bone scans should be done in follow-up for response assessments.
11. Optional biopsies: at baseline (within 2 weeks prior to first treatment) and within 2 weeks of first imaging restaging; optional biopsy at/near progression, where clinically feasible.

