6.3 RESPONSE ASSESSMENT

For the purposes of this study, during the study participants should be re-evaluated for response every 8 weeks (+/- 1 week), according to the [Study Calendar](#).

The Investigator may perform scans in addition to a scheduled trial scan for medical reasons or if the Investigator suspects PD.

Tumor assessments may include the following evaluations: physical examination (with photograph and measurement of skin lesions, as applicable); cross-sectional imaging using computed tomography (CT) or magnetic resonance imaging (MRI) scan of the skull base, neck, chest, abdomen, and pelvis; nuclear bone scan for subjects with known/suspected bone lesions; and CT of the skull base and MRI of brain (at baseline and follow ups as clinically warranted based on symptoms/findings per investigator discretion). The preferred method of disease assessment is CT with contrast. If CT with contrast is contraindicated, CT of the chest without contrast and MRI scan of the skull base, neck, abdomen/pelvis is preferred.

Radiologic imaging: Brain MRI/CT at the baseline and if needed at follow ups. CT scan of skull base, neck, chest, abdomen, and pelvis. or MRI.

In addition, PET (FDG or Dotatate) scan will be acquired at the time of first treatment response evaluation, and at/near radiographic progression, where clinically feasible. PET scan may also be acquired per investigator discretion to characterize metabolic activity of lesions (target/non-target/new) beyond cross-sectional measurement-based response categories, such as in cases of, discordant response among lesions, durable partial response, or other indeterminate radiological changes.

For each participant, the Investigator will designate 1 or more of the following measures of tumor status to follow for determining response: CT or MRI images of primary and / or metastatic tumor masses, physical examination findings, and the results of other assessments.

The measure(s) to be chosen for sequential evaluation during the trial have to correspond to the measures used to document the progressive tumor status that qualifies the subject for enrollment.

Post-baseline response assessments should follow the lesions identified at baseline. The same modality of assessment (e.g., CT) used to identify/evaluate lesions at baseline should be used throughout the course of the study unless subject safety necessitates a change (e.g., allergic reaction to contrast media).

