16 LIST OF ABBREVIATIONS

Abbreviation	Term
AACR	American Association for Cancer Research
AAO-HNS	American Academy of Otolaryngology-Head and Neck Surgery
ACAT	Ability to Consent Assessment Team
ADA	anti-drug antibodies
ADR	adverse drug reactions
AE	Adverse Event/Adverse Experience
AESI	Adverse Event/Experience of Special Interest
AHNS	American Head and Neck Society
ALT	alanine transaminase
ANC	Absolute neutrophil count
ARS	American Rhinologic Society
ASCO	American Society of Clinical Oncology
AST	aspartate aminotransferase
BARON	Bintrafusp alfa in Recurrent/Metastatic Olfactory Neuroblastoma
β-HCG	Beta human growth hormone
BSI	Biospecimen Inventory System
BTRIS	Biomedical Translational Research Information System
CAP or C/A/P	Chest, abdomen, pelvis
CBC	Complete blood count
CCR	Center for Cancer Research
CD4	cluster of differentiation 4
CD8	cluster of differentiation 8
CFR	Code of Federal Regulations
CK	Creatine kinase
CLIA	Clinical Laboratory Improvement Amendment
CN	checkpoint-naïve
CNS	Central nervous system
CONSORT	Consolidated Standards of Reporting Trials
COV	Close-out Visit
CR	checkpoint-resistant
CR	Complete Response
CSP	Clinical Services Program
CRADA	Cooperative Research and Development Agreement
CRIS	Clinical Research Information System
CRF	Case Report Form
CT	Computed Tomography
ct DNA	Circulating tumor DNA
CTCAE	Common Terminology Criteria for Adverse Events
dbGaP	database of Genotypes and Phenotypes
DNA	Deoxyribonucleic acid

Abbreviation	Term
DO	Duration of Response
ECG / EKG	Electrocardiogram
ECOG	Eastern Cooperative Oncology Group
EDTA	Ethylenediaminetetraacetic acid
ELISA	enzyme-linked immunosorbent assay)
FDA	Food and Drug Administration
FDG	fluorodeoxyglucose
FFPE	Flash frozen, paraffin embedded
EOT	End of treatment
FT4	free thyroxine
GCP	Good Clinical Practice
GLP	Good Laboratory Practices
GMB	Genitourinary malignancies branch
GMP	Good Manufacturing Practices
GOT	Glutamic oxaloacetic transaminase
GPT	glutamate pyruvate transaminase
HBV	Hepatitis B virus
HCV	Hepatitis C virus
HHS	Health and Human Services
HIV	Human immunodeficiency virus
H&P	History and Pathology
IB	Investigator's Brochure
ICBMs	immune checkpoint blockade monoclonal antibodies
ICH	International Conference on Harmonisation
iCPD	confirmed progressive disease
IHC	Immunohistochemistry
IMV	Interim Monitoring Visit
IND	Investigational New Drug
INR	International Normalized Ratio
irAE	Immune-related adverse reactions
IRB	Institutional Review Board

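### The 14.28 rem annual maximum in Section 12.5.1.3 rests on a scan list that leaves out follow-up bone scans and skull base and neck CT, which the protocol elsewhere calls for or permits

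*Combined protocol and SAP*

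**What the plan says.** Section 12.5.1.3 lists four sources of radiation:

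- CT: "Up to 7 CT scans (C/A/P) per year for disease assessment". Section 16 expands C/A/P as "Chest, abdomen, pelvis".
- PET/CT: up to 3 a year, FDG or Dotatate.
- CT-guided biopsies: 3.
- Bone scans: "Up to 2 bone scans".

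It then gives the total: "Subjects in this study may be exposed to approximately 14.28 rem maximum annually". It calls this roughly the "same amount of radiation as 47.6 years of background radiation" and attaches a 1.4% risk of cancer and a 0.7% risk of fatal cancer. A closing note says that FDG was used for the PET/CT item because its dose can be higher than that of Dotatate.

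The imaging itself is set elsewhere. Section 3.7, footnote 10, puts tumour imaging every 8 weeks. Of participants with known or suspected bone lesions who have a bone scan at screening it says: "in these cases bone scans should be done in follow-up for response assessments". Section 6.3 gives the regions as "CT scan of skull base, neck, chest, abdomen, and pelvis. or MRI" and names contrast CT as the preferred method. Section 2.2.2 lists the same regions at screening, again with MRI as the alternative. Section 6.3 also asks for a repeat scan at least 4 weeks after a first response, and waives the next scheduled scan if that is due less than 4 weeks later.

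**The concern.** A figure called a maximum should cover the heaviest imaging that the protocol allows in a year. Two items on the list look lighter than the schedule. Two bone scans cover screening and one follow-up, so a participant scanned at each response assessment passes the count at week 16. The CT item stops at the chest, although this tumour arises in the nasal cavity and Section 1.2.1 describes recurrence in the neck nodes. Section 1.2.1 also names bone among the commonest metastatic sites, so participants with bone lesions are to be expected.

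No endpoint, analysis or decision rule depends on this. What is at stake is the accuracy of a risk figure in the risk-benefit section, which may also appear in the consent document.

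**Working it through.** **1. Are the stated figures consistent with each other?** Inputs, all from 12.5.1.3: 14.28 rem, 47.6 years, 1.4%, 0.7%.

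- Background: 14.28 / 47.6 = 0.300 rem per year.
- Cancer: 14.28 x 0.1% per rem = 1.43%, which rounds to 1.4%.
- Fatal cancer: 14.28 x 0.05% per rem = 0.71%, which rounds to 0.7%.

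The conversions agree, so the question is only what went into 14.28 rem.

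**2. Can 14.28 rem be rebuilt?** With C, P, B and S as the doses per CT, PET/CT, biopsy and bone scan, 7C + 3P + 3B + 2S = 14.28. That is one equation with four unknowns, and the documents give none of the four doses. The total cannot be reproduced or corrected from the documents.

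**3. Counts in the first 52 weeks.** Screening plus weeks 8, 16, 24, 32, 40 and 48 makes 7 assessments.

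| Item | Counted in 12.5.1.3 | Schedule | Agreement |
|---|---|---|---|
| Routine body CT | 7 | 7 | Yes |
| PET/CT | 3 | 3 (screening, week 8, progression) | Yes |
| Biopsy | 3 | 3, optional (baseline, first restaging, progression) | Yes |
| Bone scan, participants with bone lesions | 2 | Up to 7 if done at each assessment | Short by up to 5 |
| Skull base and neck CT | None listed | Up to 7 if CT is used rather than MRI | Not listed |

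**4. Confirmation scans.** A partial response at week 8 confirmed at week 12 leaves the week 16 scan exactly 4 weeks away and so still due: 8 CTs. Confirmed at week 14, the week 16 scan is 2 weeks away and may be dropped: still 7. An eighth CT therefore needs early confirmation.

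**5. How much extra dose changes the stated risk?** At 0.1% per rem, 1.45% corresponds to 14.50 rem, so 14.50 - 14.28 = 0.22 rem is enough to round to 1.5%. Spread over 5 further bone scans, that is 0.22 / 5 = 0.044 rem each. With the unrounded ratio, 1.45 x 14.28 / 1.4 = 14.79 rem, so 0.51 rem is needed, or about 0.10 rem each.

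**6. Illustration only.** The doses per scan below are assumptions and do not come from the documents.

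- 5 further bone scans at 0.1 to 0.8 rem: 14.28 + 0.5 = 14.78 to 14.28 + 4.0 = 18.28 rem. That is 1.5% to 1.8%, or 49.3 to 60.9 background years.
- Those plus 7 skull base and neck CTs at 0.2 to 1.0 rem: 14.78 + 1.4 = 16.18 to 18.28 + 7.0 = 25.28 rem. That is 1.6% to 2.5%, or 53.9 to 84.3 background years.

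The width of these ranges shows that the result depends on the assumed doses.

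**The case against.** The case for leaving the figure alone has several parts.

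- Three of the four listed items match the calendar, and the conversions are sound. That stands, and it confines the point to bone scans and CT regions, with the confirmation scan secondary.
- Footnote 10 makes the screening bone scan optional and does not say that follow-up scans occur at every 8-week assessment. Seven is a possible reading, not a stated count. That stands too, but nothing in the footnote limits the number to two.
- Skull base and neck may be imaged by MRI, the assessments in 6.3 are worded as what may be included, and one clause ties skull base CT at follow-up to clinical need. So CT of these regions is not mandatory at each assessment. This does not rescue a maximum: the note in 12.5.1.3 takes the higher-dose PET option for that purpose, and by the same logic the preferred CT belongs in the total.
- The dose used for the C/A/P item might already include the neck. The documents neither show this nor exclude it.
- Footnote 10 lets responders move to imaging every 3 months. That is at the investigator's discretion, so it lowers some participants' dose but not the ceiling.
- The total already adds items that few participants would all receive in one year, since the third PET/CT and third biopsy come at or near progression. This stands against the inference that every participant with bone metastases exceeds 14.28 rem. Someone with several bone scans but no progression procedures could stay below it.

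**Conclusion.** The point holds as an inconsistency between sections. If 14.28 rem is the sum of the listed procedures, as the text implies, it is not a maximum for participants with bone lesions or for those whose skull base and neck are imaged by CT. The bone scan count is short by up to 5 in year 1, on the reading that a scan is done at each assessment. Skull base and neck CT does not appear in the list.

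The direction does not depend on assumed doses, because any omitted scan adds a positive amount. The size does. A reader might infer that a specific corrected risk, such as about 2%, can replace 1.4%. The documents give no dose per procedure, so they do not support that, and the ranges above are illustrations. Nor do they support reading the whole list as short, or the confirmation scan as always adding an eighth CT.

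Whether the consent document is affected cannot be seen. The note in 12.5.1.3 shows only that it uses FDG for the PET item, not which scan counts it uses.

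**What to change.** Reconcile Section 12.5.1.3 with Sections 2.2.2, 3.7 (footnote 10) and 6.3 on three items: the number of bone scans for participants with bone lesions, the CT regions covered, and whether a confirmation scan can add to the seven CTs. The sponsor should decide which text reflects its intention. Either the dose list is brought into line with the schedule, or the schedule text is clarified so that it matches the list.

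Then recalculate from the agreed counts, show the dose assumed per procedure so that the total can be checked, and restate the rem, background-year, cancer-risk and fatal-cancer figures together. Carry the same figures into the consent document if it uses the same counts.

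The cost is one recalculation and a wording change. If the schedule is the text that stands, no procedure changes and the stated risk becomes slightly less favourable.

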12.5.1.4 Risks Due to Contrast Agents for CT

Contrast agents can cause allergic reactions and kidney damage. Allergic reactions can include mild itching associated with hives but can also result in a serious life-threatening emergency from difficulty breathing. If this occurs, it is treatable.

